11.0 Study Timelines

11.1 Describe the anticipated duration needed to enroll all study subjects.

Response: Participants will be enrolled fall of each year.

11.2 Describe the duration of an individual subject's participation in the study. Include length of study visits, and overall study follow-up time.

Response: Participants will be invited to a 3-hour intake visit to have study eligibility and screening procedures completed. Participants will enroll in the study for the entire school year as random assignment and assessment/study procedures will be implemented starting in January and continued until May.

11.3 Describe the estimated duration for the investigators to complete this study (i.e. all data is collected and all analyses have been completed).

Response: All data and analyses should be completed for this study by summer 2022.

12.0 Setting

12.1 Describe all facilities/sites where you will be conducting research procedures. Include a description of the security and privacy of the facilities (e.g. locked facility, limited access, privacy barriers). Facility, department, and type of room are relevant. Do not abbreviate facility names.

NOTE: Examples of acceptable response may be: "A classroom setting in the Department of Psychology equipped with a computer with relevant survey administration software," "The angiogram suite at Buffalo General Medical Center, a fully accredited tertiary care institution within New York State with badge access," or, "Community Center meeting hall."

Response: University at Buffalo Site. Research activities will be conducted within the context of the Center for Children and Families (CCF) at the University at Buffalo (SUNY). The CCF is an interdisciplinary center that focuses on a tripartite mission of education, research, and service. The CCF is a research, clinical, and training facility and its goals are to advance knowledge of mental health and learning problems. It is a 12,000 square foot clinical research facility that consists of two children's classrooms (with observational windows), five clinical rooms (with observational windows), waiting rooms, a journal library, copy room, and offices. All offices are equipped with telephones and networked computers. A large number of current statistical software packages are available to researchers, and statistical consultation is available. Also, all the required assessment materials are housed in the CCF. CCF staff includes Ph.D. level faculty, graduate trainees in clinical psychology and school psychology, full-time research staff, and undergraduate trainees. Faculty from numerous departments and schools across the university are affiliated with the CCF. Located in Buffalo, the CCF is close to local schools.

12.2 For research conducted outside of UB and its affiliates, describe:

- *Site-specific regulations or customs affecting the research*
- *Local scientific and ethical review structure*

NOTE: This question is referring to UB affiliated research taking place outside UB, i.e. research conducted in the community, school-based research, international research, etc. It is not referring to multi-site research. UB affiliated institutions include Kaleida Health, ECMC, and Roswell Park Cancer Institute.

Response: A considerable amount of research activities will occur within classrooms in local school districts. Prior to engaging in any research activities within classrooms, the principal investigator will obtain a Permission to Conduct Research in Schools form from a leader in the school and/or district. These permission forms will be kept on file and submitted to the IRB during annual reviews or amendment requests.

N/A: This study is not conducted outside of UB or its affiliates.

13.0 Community-Based Participatory Research

13.1 Describe involvement of the community in the design and conduct of the research.

NOTE: Community-Based Participatory Research (CBPR) is a collaborative approach to research that equitably involves all partners in the research process and recognizes the unique strengths that each brings. CBPR begins with a research topic of importance to the community, has the aim of combining knowledge with action and achieving social change to improve health outcomes and eliminate health disparities.

Response:

N/A: This study does not utilize CBPR.

13.2 *Describe the composition and involvement of a community advisory board.*

Response:

N/A: This study does not have a community advisory board.

14.0 Resources and Qualifications

14.1 *Describe the qualifications (e.g., education, training, experience, expertise, or certifications) of the Principal Investigator and staff to perform the research. When applicable describe their knowledge of the local study sites, culture, and society. Provide enough information to convince the IRB that you have qualified staff for the proposed research.*

NOTE: If you specify a person by name, a change to that person will require prior approval by the IRB. If you specify a person by role (e.g., coordinator, research assistant, co-investigator, or pharmacist), a change to that person will not usually require prior approval by the IRB, provided that the person meets the qualifications described to fulfill their roles.

Response: [name]., Principal Investigator. [name] is Professor in the Department of Counseling, School, and Educational Psychology at the University at Buffalo, SUNY. Academic year (9 mos) salary support is requested at 20% and 20% summer salary support is requested in Years 1-4. His expertise is in the area of school-based behavioral treatments for children with ADHD, and he was principal investigator on the Goal 2 project that investigated how DRCs could be used to enhance IEP implementation as well as a Co-Investigator on the prior Adaptive Treatment study (Preliminary Study 6). [name] has extensive experience with classroom-based behavioral interventions in both analogue and regular school settings as well as in the measurement of classroom-based teacher and student outcomes (i.e., he was co-I on two IES Goal 5 studies). [name] will serve as principal investigator for this project at the Buffalo site, and he will be responsible for all research and project implementation. At the Buffalo site, he will oversee recruitment of participants, coordinate assessments, and provide supervision of research staff. During the final year of the project, he will

participate in analyzing and interpreting the results and in writing reports and publications.

Describe other resources available to conduct the research.

14.2 *Describe the time and effort that the Principal Investigator and research staff will devote to conducting and completing the research.*

NOTE: Examples include the percentage of Full Time Equivalents (FTE), hours per week. The question will elicit whether there are appropriate resources to conduct the research.

Response: [name] time is budgeted *Academic year (9 mos) salary support is requested at 22% and 25% summer salary support is requested in Years 1-4.*

14.3 *Describe the availability of medical or psychological resources that subjects might need as a result of anticipated consequences of the human research, if applicable.*

NOTE: One example includes: on-call availability of a counselor or psychologist for a study that screens subjects for depression.

Response: Study PI ([name]) will be available on-call for participants throughout the study via cell-phone.

14.4 *Describe your process to ensure that all persons assisting with the research are adequately informed about the protocol, the research procedures, and their duties and functions.*

Response: All study staff will complete CITI training, complete UB's training for working with children and have a background check completed to ensure the appropriateness for working with children.

15.0 Other Approvals

15.1 *Describe any approvals that will be obtained prior to commencing the research (e.g., school, external site, funding agency, laboratory, radiation safety, or biosafety).*

Response: Any participating school district will complete the Permission to Complete Research in Schools form prior to any classroom visits or research conducted in the school.

 N/A: This study does not require any other approvals.

16.0 Provisions to Protect the Privacy Interests of Subjects

16.1 Describe how you will protect subjects' privacy interests during the course of this research.

NOTE: Privacy refers to an individual's right to control access to him or herself. Privacy applies to the person. Confidentiality refers to how data collected about individuals for the research will be protected by the researcher from release. Confidentiality applies to the data.

Examples of appropriate responses include: "participant only meets with a study coordinator in a classroom setting where no one can overhear", or "the participant is reminded that they are free to refuse to answer any questions that they do not feel comfortable answering."

Response: During all interactions with parents, only first names will be used, not last names. When meeting with teachers, we will not tell office staff about the specific nature of our visit. All intake and follow-up appointments will occur in private, secure offices at the University at Buffalo or at private locations at the schools. Any correspondence to participant families or teachers will be mailed in sealed envelopes.

16.2 Indicate how the research team is permitted to access any sources of information about the subjects.

*NOTE: Examples of appropriate responses include: school permission for review of records, consent of the subject, HIPAA waiver. This question **does apply** to records reviews.*

Response: Only graduate students, direct study staff, and the principal investigator will have access to those rooms and cabinets where the data will be stored. Undergraduate research assistants will have access to the data initially for entry into a computerized database, but this will all be monitored and controlled by the graduate students, direct study staff, or principal investigator. School related data (e.g., teacher rating scales) will be obtained from the school via a Release of Information Authorization signed by the parent.

17.0 Data Management and Analysis

17.1 Describe the data analysis plan, including any statistical procedures. This section applies to both quantitative and qualitative analysis.

Response: To ensure appropriate manipulation of the independent variable the treatment integrity data described above will be collected and analyzed. The distributional characteristics of all dependent variables will be examined. If outcomes are appreciably non-normal, we will consider power transformations where appropriate. Although we expect that our cross-site and cross-cohort training efforts will mitigate the possibility of any site, cohort, or consultant differences, we will still conduct sensitivity analyses that evaluate treatment effects separately by cohort, site, and

consultant. As the study is powered for efficacy analyses and we do not anticipate being powered to detect cohort/site/consultant effects, these analyses will emphasize effect size comparisons. To the extent that any differences are revealed, we will improve cross-site and cross-cohort training and fidelity observations, as well as to consider the inclusion of site, cohort, or consultant as additional covariates. Benjamini-Hochberg adjustments will be used throughout in order to control for the false discovery rate associated with multiple comparisons across outcomes (Benjamini & Hochberg, 1995). This strategy is implemented in SAS® using PROC MULTTEST. Multiple imputation methods will be used to accommodate missing data (Allison, 2002). This strategy is implemented in SAS® using PROC MI and MIANALYZE.

Aim 1. Investigate the effectiveness of using a DRC to link the child with ADHD's IEP to daily classroom behavior.

Aim 1 will be evaluated using Analysis of Covariance (ANCOVA) models of the following form

$$y_{post} = \gamma_1 \text{pretest} + \gamma_2 \text{DRC} + \sum_{j=1}^5 \gamma_j \text{covariates} + e_i$$

Specifically, each outcome score will be regressed on the corresponding pre-test score, a treatment indicator, and four covariates (medication status, grade level, comorbid DBD, and child gender)—the first three of which will be evaluated as potential moderators of treatment in Aim 2. Although the pretest score can be conceived as simply another covariate, it is distinguished here to emphasize the point that its inclusion results in improved statistical power relative to a repeated measures approach for evaluating treatment efficacy (Van Breukelen, 2006). Group differences on adjusted post-test scores (i.e., the significance test of γ_2) will inform the efficacy of using the DRC to enhance academic performance and behavioral outcomes beyond that associated with the routine use of IEP. Measures of primary outcome will be observations of classroom behavior and teacher ratings of academic performance. Measures of secondary outcome will include teacher ratings of symptoms and impairment related to ADHD.

Aim 2. Investigate moderators of treatment outcome.

Aim 2 will be evaluated by extending the ANCOVA model from Aim 1 as follows

$$\gamma_{post}$$

[figure not shown]
$$= \gamma_1 pretest + \gamma_2 DRC + \sum_{j=1}^2 \gamma_j covs \\ + \sum_{k=1}^3 \gamma_k moderator + \gamma_k moderator * DRC + e_i$$

Specifically, Aim 2 will extend the models estimated from Aim 1 by including three additional terms (i.e., the product of each of the three moderators—age group, comorbid DBD, IEP Quality—with the indicator of treatment). Tests of each of these three terms (i.e., $\gamma_{k1}, \gamma_{k2}, \gamma_{k3}$) will inform Aim 2. Each DRC X moderator term that is statistically significant will be probed using simple main effects (i.e., comparisons between DRC and SAU outcomes within each level of the moderator variable) in order to delineate the differential magnitude of treatment on adjusted post-test scores as a function of a given covariate (i.e., primary vs. secondary grade; ADHD only vs. ADHD+DBD; High Quality vs. Low Quality IEP).

Aim 3. Investigate mediators of treatment outcome. Aim 3 will be evaluated using a path analytic approach for testing mediation. The path model will extend the ANCOVA models above by simultaneously

estimating equations for both the post-test score and mediators. Specifically, a path model will be estimated in which post-test scores are regressed on a dichotomous indicator of treatment, covariates described above (including pre-test scores and moderators), and on three mediators, measured as aggregate variables across the treatment period, including the quality of the classroom environment (ratio of positive to negative comments direct to the target child), consistency of teacher feedback in the classroom and home-based consequences related to school behavior. Moreover, the mediators will be simultaneously regressed on the indicator of treatment. A prototypic model is depicted below. The dashed line from covariates to post-test indicates that this actually refers to a block of variables that are omitted for presentation purposes A formal evaluation of mediation comes from

tests of whether the product of the coefficients relating treatment to mediators and mediators to outcomes (i.e., the indirect effects) differs from 0 (Bollen, 1987; MacKinnon, 2008). Whereas the joint test of the set of product terms (i.e., $a*d = b*e = c*f = 0$) provides an omnibus test of mediation, individual tests of products (i.e., $a*d = 0; b*e = 0; c*f = 0$) informs the contribution of each specific mediator. When combined with information regarding tests of indirect effects, the statistical significance

of the direct effect of treatment on post-test scores informs whether partial (i.e., if the path 't' is statistically significant) or complete (i.e., if the path 't' in the figure is not statistically significant) mediation is present. All tests of mediation will be based on the use of bootstrapped standard errors, which results in better statistical power and avoids having to make potentially unrealistic distributional assumptions about the mediated effect (MacKinnon et al., 2004; Preacher & Hayes, 2008). All mediated effects will be tested using Mplus software which includes facilities for testing individual and compound sets of mediated effects, as well as the use of bootstrapped standard errors (Muthén & Muthén, 2006).

17.2 If applicable, provide a power analysis.

NOTE: This may not apply to certain types of studies, including chart/records reviews, survey studies, or observational studies. This question is asked to elicit whether the investigator has an adequate sample size to achieve the study objectives and justify a conclusion.

Response: We relied on our previous ($N = 63$), randomized study contrasting DRC and SAU conditions in order to compute effect sizes for the proposed study (see Preliminary Study 2). Results from that study indicated an effect size of approximately Cohen $d = .50$ (or larger) across the majority of outcomes considered. The weighted random effects effect size of between groups studies for ADHD such as this one was $.74$; thus we are using a conservative effect size relative to the larger literature ([name] et al., 2009). We also assumed that covariates (most prominently the pre-test score) would explain at least 45% of the observed variation in post-test scores (in the Goal 2 study using comparable covariates 47% of the variance for post-test scores for objective observations and teacher ratings of ADHD was explained by pre-test scores).

Given these assumptions, Aim 1 will have power of $.80$ to detect effects of Cohen $d = .50$ with $N = 71$ participants. In order to estimate power for Aim 2, we assumed treatment effects of Cohen $d = .4$ and $.6$ within moderator groups (e.g., the treatment effect would be Cohen $d = .4$ in intermediate grades compared to Cohen $d = .6$ in primary grades), which, given the sampling plan that balances participants across levels of dichotomous moderators, is consistent with the marginal treatment effect of Cohen $d = .50$ used for Aim 1. In order to detect treatment effects as small as Cohen $d = .40$ (given $R^2 = .45$, as per Aim 1) with power of $.80$, $N = 105$ participants are necessary. Hence, the total sample size needed to power Aim 2 at $.80$ is adequate at $N = 216$ (i.e., 108 participants $\times 2$ levels of moderator). Based on recent work by Fritz and MacKinnon (2007), the proposed total sample size of 216 will provide power of greater than $.80$ to detect moderate sized indirect (mediated) effects (there is no standard metric for reporting effect sizes for indirect effects). We

conclude that N=216 participants results in power of .80 or greater to address all three motivating aims. The use of modern methods for dealing with missing data (Multiple Imputation for Aims 1 and 2, Full Information Maximum Likelihood estimation for Aim 3) ensure that all N = 216 participants will contribute to each analysis.

17.3 Describe any procedures that will be used for quality control of collected data.

Response:

Treatment Integrity and Fidelity of the Consultant Activities

Consultants will partner with teachers/parents to develop DRCs based on the IEP of the participating student. Procedures for establishing DRCs are manualized (see Appendix D) and all visits with teachers and parents have a checklist that is to be completed by the consultant to ensure all procedures were implemented (see Appendix C). Further, to ensure that the consultant checklists are being completed appropriately, we will have consultants audio-record all consultant meetings, and 20% of each consultant's recordings will be evaluated for integrity to the checklists (all meetings will be recorded to prevent reactivity or positive presentation solely during selected recorded sessions). In prior work we were able to obtain permission from 100% of teachers to audiotape comparable meetings (N=89; [name], Reddy, et al., 2017). To obtain information on the fidelity of consultants we will ask parents and teachers to complete an evaluation of the consultant following the final assessment through submission of a sealed envelope to a staff member uninvolved with the case to prevent reactivity. Adherence will be measured by contact logs and the collection of behavioral products (e.g., completed DRCs).

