4.0 Study Design

4.1 Describe and explain the study design (e.g. case-control, cross-sectional, ethnographic, experimental, interventional, longitudinal, observational).

Response: This project will use a randomized, between group design. The sequence of recruitment, randomization, and assessment is summarized in the Figure below. After informed consent and assent is obtained, and completion of the intake and review of inclusion and exclusionary criteria, the child will be randomly assigned to one of two groups. Participants will be randomly assigned to either (1) School as Usual (SAU) or (2) Daily Report Card (DRC), with 108 participants per group. The recruitment plan will aim for an equal number of subjects in the DRC and SAU groups, and participants will be

stratified within randomization across potential moderator variables including medication and grade level.

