5.0 Local Number of Subjects

5.1 *Indicate the total number of subjects that will be enrolled or records that will be reviewed locally.*

Response: The total sample will include 216 participants (108 at the Buffalo site and 108 at the Miami Site).

5.2 *If applicable, indicate how many subjects you expect to screen to reach your target sample (i.e. your screen failure rate).*

Response: We expect to screen three times as many subjects as are needed to meet recruitment goals. Our estimate is we will screen 700 participants in order to obtain the targeted sample size of 216.

5.3 *Justify the feasibility of recruiting the proposed number of eligible subjects within the anticipated recruitment period. For example, how many potential subjects do you have access to? What percentage of those potential subjects do you need to recruit?*

Response: Using the Common Core of Data (<http://nces.ed.gov>) information from the 2011-12 school year, the western New York district represents approximately 16,694 students in grades K-6 and the south Florida district includes approximately 186,467 students in these grades. Using the same database, it is estimated that 4174 students (Buffalo site) and 18,647 (Miami site) in these grades have IEPs. Given our pilot work ([name], Naylor et al., 2009) and the work of Forness & Kavale (2002), it is further conservatively estimated that approximately 25% of these students in special education will have ADHD, yielding a total sample of 1,044 students in Buffalo and 4,662 students in Miami eligible to be screened for participation in each year. These estimates suggest for our study recruitment plan of enrolling 36 children per site, per year, we need to enroll 3% of children at the Buffalo site and 0.8% at the Miami site in the total pool of potential participants during each of the study years. These estimates indicate our recruitment plan is feasible.

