The recruitment plan will aim for an equal number of subjects in the DRC and SAU groups, and participants will be block randomized across potential moderator variables including medication and grade level. In the Goal 2 study, for which these variables were unselected, 52% of the final sample was prescribed medication and 66% were in grades K-3 and 34% were in grades 4-6. Thus, it appears that the plan to have an equal number of subjects in each block is feasible with careful attention to recruiting participants in the older grades in the present application. Block randomization based on child psychoactive medication status will promote equal distribution of participants across this variable. The medication variable will be defined as “no medication” if the child is not prescribed psychoactive medication immediately prior to randomization and as “taking medication” if the child is prescribed psychoactive medication and it is being actively administered at the time of randomization. In sum, an equal number of participants (N=72/year) will be enrolled in four blocks each year (i.e., No medication/Primary grade; No medication/Intermediate grade; Taking medication/Primary grade; Taking medication/Intermediate grade). Random assignment will be conducted following the completion of all baseline measures by a blinded member of the study team ([name]). Following randomization, a form letter will be generated that informs the study staff and participating family of group

assignment. Consultants will then be randomly assigned to the case with an equal number of DRC and SAU cases assigned to each consultant.

For those students who are medicated with stimulant medication, we will ask parents to obtain permission from the child's doctor to withhold medication for the assessment days in January and May so as to collect information on the child's behavior when unmedicated.

Intervention Groups

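### Site and cohort should be fixed covariates in the Aim 1 and Aim 2 models, not additions considered after effects split by site, cohort and consultant have been inspected

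*Combined protocol and SAP*

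**What the plan says.** **Model.** In Section 17.1 the Aim 1 ANCOVA regresses each post-test score on its pretest, a treatment indicator and four named covariates: medication status, grade level, comorbid DBD and gender. Aim 2 adds moderator terms. Neither model names site, cohort or consultant.

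**Trigger.** The same section estimates treatment effects separately by cohort, site and consultant as sensitivity analyses. It compares them by effect size and concedes that the trial is not expected to have power for such differences. If any appear, two actions follow: "we will improve cross-site and cross-cohort training and fidelity observations", and the team will "consider the inclusion of site, cohort, or consultant as additional covariates". No test, threshold or timing is given.

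**Design.** Section 5.1 gives the sample as "108 at the Buffalo site and 108 at the Miami Site", and Section 5.3 plans on "enrolling 36 children per site, per year". In Section 4.1 participants are "stratified within randomization across potential moderator variables including medication and grade level". Section 10.1 adds that "an equal number of participants (N=72/year) will be enrolled in four blocks each year" and lists the four blocks as medication by grade. Site is not among them. Section 10.1 also has consultants appointed at each site, assigned after randomisation, with equal DRC and SAU cases per consultant.

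**The concern.** Site and cohort are fixed by the recruitment plan and known before any outcome is seen, so whether to adjust for them can be settled in advance. The plan instead ties the decision to the observed treatment effects.

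That raises two problems. The first is logical. Differing treatment effects across sites are a site-by-treatment interaction. A site main effect absorbs differences in outcome level between sites and leaves the interaction where it was. Conversely, adjusting for level is worthwhile whether or not treatment effects differ. The second is statistical. Comparisons without power will often show differences when none exist, so the choice of model would rest largely on chance.

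At stake are a primary model that is not fixed before the data are seen, and some precision if the two districts or the yearly cohorts differ in outcome after pretest adjustment.

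**Working it through.** **Inputs.** N = 216, with 108 per site (Section 5.1) and "with 108 participants per group" (Section 4.1). There are 72 children per year (Section 10.1), so 216/72 = 3 cohorts. Covariate R² = 0.45 (Section 17.2), so residual variance is 0.55 in units of the outcome's total SD. The documents give neither alpha nor sidedness; two-sided 0.05 is assumed.

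**1. The plan's own figures.** Total N = 4 × (1.96 + 0.842)² × 0.55 / d². For d = 0.50 this is 69.1, or 70 at 35 per arm (stated: 71). For d = 0.40 it is 107.9, or 108 (stated: 105). Both are reproduced closely, so 0.55 is the right residual variance to carry forward.

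**2. Noise in the site comparison.** The SE of one site's effect is √(4 × 0.55/108) = 0.143. The SE of the difference between two sites is 0.143 × √2 = 0.202, with 95% limits 1.96 × 0.202 = 0.40. With identical true effects, the observed difference exceeds 0.1 SD in 62% of trials, 0.2 SD in 32% and 0.3 SD in 14%. Power to detect a real difference of 0.2 SD (0.4 versus 0.6) is 17%.

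**3. Noise in the cohort comparison.** The SE of one cohort's effect is √(4 × 0.55/72) = 0.175. The range over three cohorts has a median of 0.28 SD under identical true effects and exceeds 0.2 SD in 70% of trials.

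**4. How often the trigger fires by chance.** The plan gives no threshold; 0.2 SD is assumed here. Treating the two comparisons as independent gives 1 − (0.68 × 0.30) = 0.80. Simulation gives 0.79. The number of consultants is not stated, so no figure is given for them.

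**5. Consequences.** Simulation used 6,000 trials per scenario, with arms balanced within year and block but not within site. All shifts are assumptions. The site shift is the difference between site means after pretest adjustment, and the cohort shift is the SD of cohort means. The trigger threshold is 0.2 SD.

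| Site / cohort shift (SD) | Type I error: never adjust / trigger / always | Power at d = 0.30: never / trigger / always |
|---|---|---|
| 0 / 0 | 0.054 / 0.054 / 0.052 | 0.846 / 0.845 / 0.844 |
| 0.25 / 0.1 | 0.051 / 0.051 / 0.052 | 0.832 / 0.839 / 0.844 |
| 0.5 / 0.2 | 0.046 / 0.049 / 0.052 | 0.788 / 0.814 / 0.844 |
| 0.8 / 0.3 | 0.038 / 0.046 / 0.052 | 0.697 / 0.769 / 0.844 |

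Monte Carlo SE for type I error is about 0.003. Picking the smallest p-value among the models that the trigger opens gives 0.055 to 0.056.

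An analytic check on the third row: a site shift of 0.5 adds 0.5²/4 = 0.0625 to the residual variance. The SE ratio is then √(0.6125/0.55) = 1.055, against a simulated ratio of 0.1073/0.1015 = 1.057.

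**6. Cost of always adjusting.** The model goes from 6 to 9 terms besides the intercept (site 1, cohort 2), so residual degrees of freedom fall from 209 to 206. Power at N = 216 is 0.9985 before and after for d = 0.50, and 0.976 before and after for d = 0.40.

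**7. Arm balance within site.** If only the listed blocks restrict allocation, the DRC count at a 108-child site has an SD of about 3.7 and a 95% range of 47 to 61 (hypergeometric).

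**The case against.** The strongest reply is that the plan already has a fixed model. Aim 1 names its covariates, the split analyses are labelled sensitivity analyses, and the wording commits only to consider additions. Medication and grade, the two named stratification factors, are in the Aim 1 model, and cohort is in effect a randomisation layer because the blocks are filled each year. This narrows the point to site and cohort as omitted covariates. It does not remove it, because the same section leaves the model open to revision after results by site are seen.

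A reader might infer three stronger charges.

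- **Inflated type I error.** The simulation does not bear this out: 0.046 to 0.054 under the trigger, and at most about 0.056 when the smallest p-value is chosen.
- **Bias from site imbalance.** Randomisation keeps the estimate unbiased; chance imbalance is sampling variance. The range of 47 to 61 is also close to a worst case. If each site-based consultant does carry equal DRC and SAU cases, each site is nearly balanced. That commitment presumes balance and does not create it, because consultants are assigned after allocation. The fair criticism is that allocation within site is unclear. Section 5.3 shows that the districts differ in size (16,694 versus 186,467 pupils) and in IEP share (4,174/16,694 = 25% versus 18,647/186,467 = 10%). Nothing shows that outcomes differ after pretest adjustment.
- **Outcomes by arm shown to the team mid-trial.** Improving training implies some use before the end, but Section 17.1 gives no timing and Section 19.1 calls the yearly analyses blind. The documents do not establish that such results would be seen.

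The Aim 1 formula sums five covariates where the text names four. The fifth is unlikely to be site: the Aim 2 formula has two covariates and three moderators, one of them IEP quality, which accounts for five.

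**Conclusion.** The point holds as a modest one. The trigger tests the wrong thing, fires mostly by chance, and leaves the primary model unsettled. The noise figures (SE 0.20 SD, 95% limits 0.40) rest only on the plan's sample size and R². The 79% rate rests on an assumed 0.2 SD threshold.

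The precision loss depends on assumed site and cohort differences. Prespecified adjustment gains nothing if there are none. At shifts of 0.5 and 0.2 SD, power at d = 0.30 rises from 0.79 unadjusted and 0.81 under the trigger to 0.84. At the planned d = 0.50 power is ample either way. Validity of the Aim 1 test is not in question. This is a nearly free improvement.

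**What to change.** 1. In Section 17.1, always include site (1 df) and cohort (2 df) as fixed covariates in every Aim 1 and Aim 2 model, and delete the data-dependent trigger.
2. Keep effects split by site, cohort and consultant as end-of-trial description or sensitivity analysis, and say that they do not alter the primary model. State there how consultant is handled.
3. Base any retraining during the trial on the monthly integrity and fidelity observations (Section 10.2) and the consultant recordings (Section 17.3), not on outcomes by arm.
4. State whether randomisation is run within site. If it is, give the block scheme: 36 children per site-year over four blocks is nine per cell, which cannot split equally.

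The cost is SAP wording and three of about 209 residual degrees of freedom. The sample size does not change.
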